3.2 Part A: Trametinib Dose-Determination

Part A is a repeat dose, dose escalation monotherapy study that will identify the RP2D on the continuous dosing schedule using a 3 + 3 dose-escalation procedure. The goal of the study is to find a RP2D based on PK criteria (PK target dose), defined as achieving in children a steady state (Day 15) mean trough concentration (C_{τ}) of trametinib that is equivalent to a mean steady state (Day 15) trough concentration of 10 ng/mL trametinib observed in adults at the recommended dose of 2 mg once daily.

During dose escalation, children will be closely monitored for drug-related toxicity. If MTD is determined, the RP2D will be defined by the MTD rather than by PK criteria.

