1.2.1 Pharmacokinetics of Trametinib in Humans

Trametinib pharmacokinetic (PK) parameters were determined after single- and repeat-dose oral administration. Trametinib was absorbed rapidly, requiring 1.5 hr to reach the maximum concentration (T_{max}) after single oral administration under fasting conditions. The absolute oral bioavailability of a single trametinib 2 mg tablet is moderate to high (72%) relative to a co-administered intravenous microdose. Single-dose administration of trametinib with a high-fat, high-calorie meal resulted in a 70% decrease in maximum observed concentration (C_{max}) and a 10% decrease in area under the concentration-time curve from time zero (pre-dose) extrapolated to infinity [$AUC(0-\infty)$] compared to fasted conditions.

Following repeat-dosing, the mean area under the concentration-time curve over the dosing interval ($AUC_{0-\tau}$) and C_{max} increased in a dose proportional manner. Trametinib accumulates with repeat dosing, with a mean accumulation ratio at the recommended dose of 2 mg once daily of 5.97. Terminal half-life is 5.3 days, determined after single dose administration. Steady state is achieved by Day 15, with little difference in pre-dose (trough) concentration at the end of the dosing interval (C_{τ}), C_{max} and area under the concentration-time curve from time zero (pre-dose) to 24 hr [$AUC(0-24h)$] between Day 15 and Day 21. In adults receiving trametinib 2 mg daily for 15 days ($n=13$) the geometric mean (Coefficient of variation [CV] %) $AUC(0-24h)$ was 370 (22%) ng•hr/mL, C_{max} 22.2 (28%) ng/mL, T_{max} 1.75hr (range 1-3hr), and C_{τ} 12.1 (19%) ng/mL. (Infante, 2012). It is important to note that the 95% confidence interval (CI) associated with the adult mean of C_{τ} 12.1 ng/mL was 10.86 to 13.4 ng/mL. The lower bound of the 95% CI (approximately 10 ng/mL) of the adult mean C_{τ} will be utilized to guide the recommended Phase 2 dose in the current study.

The oral liquid formulation (0.05 mg/mL) had similar bioavailability to the trametinib tablet formulation. Single dose administration of trametinib as a 2 mg oral solution compared to the oral tablet resulted in a 12%, 10% and 71% increase in $AUC(0-\infty)$, $AUC(0-last)$, and C_{max} , respectively.

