3.2.1 Trametinib Dose Levels

The starting dose of trametinib (0.0125 mg/kg/day) is 50% of the recommended fixed dose in adults (2 mg once daily) based on an 80 kg adult ([Table 3-1](#)). In adults (n=2) after 15 days of continuous trametinib dosing (1 mg administered orally [PO] daily), the individual steady state C_{τ} was 8.44 and 19.1 ng/mL. The lowest trough concentration associated with an objective response in adults with melanoma was approximately 7 ng/mL; one complete response (1 mg dose) and one partial response (0.5 mg dose) were observed out of 12 subjects with C_{τ} of 7 ng/mL.

The second dose level (0.025 mg/kg/day) is equivalent to the recommended dose in adults (2 mg PO daily). In adults (n=13) receiving this dose, the Day 15 mean steady state C_{τ} was 12.1 ng/mL (range 8.26-16.9; 95% CI=10.86-13.4). In adults trametinib 2 mg PO daily on a continuous schedule is not associated with dose limiting toxicity and PK-PD modelling in adults with melanoma predict that 79% of subjects would exceed the mean target trough concentration over the entire dosing interval.

The third dose level (0.040 mg/kg/day) is equivalent to the MTD in adults (3 mg PO daily).

In the absence of establishing a pediatric MTD, if the PK target (Day 15 $C_{\tau} \geq 10$ ng/ml) is not achieved at the maximum dose level of 0.04 mg/kg/day, safety and PK data will be examined to consider amending the protocol for inclusion of additional higher dose levels.

Table 3-1 Trametinib Dose Levels for Part A

	Trametinib Oral Dosing
Dose Level 1 – Starting Dose	0.0125 mg/kg/day
Dose Level 2	0.025 mg/kg/day
Dose Level 3	0.04 mg/kg/day
Additional Dose Levels	Protocol amendment to explore additional dose according to observed PK values relative to target concentrations

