Detailed PK sampling will be required on Day 15 for trametinib (see [Section 7.4.1](#)). Subjects who have a day 15 trametinib $C_{\tau} < 10$ ng/mL will be considered to have failed to reach the PK target. If more than 1 out of 3 to 6 patients at a dose level have failed to reach the PK target, and MTD criteria have not been met, dose escalation will continue. The Day 15 trametinib C_{τ} of all subjects in a dose level cohort will be compared to the target C_{τ} (10 ng/mL) in adults who were treated with the recommended dose in adults. In the absence of an MTD, the RP2D will be the PK target dose defined as the dose that meets the PK criteria for adequate exposure (Day 15 trametinib $C_{\tau} \geq 10$ ng/mL in at least 80% of subjects in a cohort of at least 6 subjects (i.e.; 5/6 subjects) treated at that dose level ([Appendix 9](#)).

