3.2.6 Part A Extension: Intermediate Trametinib Dose Exploration

Preliminary trametinib PK analysis of 52 patients at the 0.025 mg/kg/day dose level from Parts A, B and C of this study (data cut-off 31-Oct-2016) indicated that the median trametinib C_{τ} was 8.2 ng/mL (< 10 ng/mL) in patients < 6 years old, whereas the median trametinib C_{τ} was 11.7 ng/mL in patients 6 years of age and older. A dose of 0.04 mg/kg/day exceeded the MTD and was not well tolerated across age categories. An intermediate dose of 0.032 mg/kg/day will be explored in patients under 6 years of age in an effort to achieve a C_{τ} similar to that achieved in adults (> 10 ng/mL) without exceeding the MTD in this age group. This is the only additional dose level intended for this age group. Using the DLT definition provided in [Section 3.2.3](#) RP2D will be declared based on safety and tolerability. The 0.032 mg/kg/day dose may replace the previously determined RP2D of 0.025 mg/kg/day for trametinib monotherapy for patients under 6 years of age.

- Initially, three patients will be enrolled at the intermediate dose level (0.032 mg/kg/day) and observed for DLT (dose determining cohort).
- If 0 DLTs are noted, then 0.032 mg/kg/day will be declared the new trametinib monotherapy RP2D for patients under 6 years of age, and 9 more patients enrolled to further characterize the PK of this dose in this age group.
- If 1 DLT is observed in the initial 3 patients, then three additional patients will be enrolled into the dose determining cohort. If no additional DLTs are observed (i.e., a total of 1 DLT in first 6 patients), then 0.032mg/kg/day will be declared the RP2D for trametinib monotherapy for patients under 6 years of age, and 6 more patients will be enrolled to further characterize the PK of this dose in this age group.

- If 2 or more DLTs are observed in the first 3 (or 6) patients in the dose determining cohort, no further patients will be enrolled at that dose and 0.032 mg/kg/day will have exceeded the MTD, and 0.025 mg/kg/day will be confirmed as the RP2D for trametinib monotherapy in this age group.

PK samples will be collected on Day 15 and Day 22.

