3.9.3 Rationale for Dose

3.9.3.1 Trametinib

The targeted dose and schedule of trametinib is based on the adult clinical dose and schedule required to achieve therapeutic benefit in BRAF mutant melanoma. In adults, the mean (range) AUC(0- τ) following repeat dosing of 1 and 2 mg once daily was 175 ng•hr/mL (107-243 ng•hr/mL) and 360 ng•hr/mL (204-536ng•hr/mL), respectively. The mean (range) C τ following repeat dosing of both the 1 and 2 mg once daily doses were 13.8 (n=2, 8.44 and 19.1 ng/mL) and 12.1 ng/mL (n=13, 8.3-16.9 ng/mL, CV=19%, 95%CI=10.86-13.4), respectively. The lowest C τ concentration associated with an objective response was approximately 7 ng/mL, where 1 complete response (CR) (1 mg dose) and 1 partial response (PR) (0.5 mg dose) were observed of 12 subjects with C τ of 7 ng/mL.

Given the safety and tolerability observed at the adult dose of 2 mg once daily and the variability associated with the mean adult trough concentration (95%CI=10.86-13.4), therapeutic benefit in pediatric subjects may be achieved by attaining trough concentration at steady state (day 15 C τ \geq 10 ng/mL) that is similar to those achieved in adults at the recommended dose. In the absence of DLT, if the PK exposure (C τ) is significantly lower than those achieved in adults, higher doses for subsequent cohorts may be modified in a protocol amendment in order to achieve PK target during dose escalation.

The starting dose in the pediatric population will be based on 1 mg as given to average 80 kg adult subject (0.0125 mg/kg) which is 50% of the recommended and FDA approved dose in adults. Steady state trough concentration (Cycle 1 Day 15 C τ (trough) data for trametinib from adults will be compared to PK data in the pediatric subjects and will guide pediatric dose recommendations. Exposure and Day 15 C τ will be assessed in-stream during the study. PK sampling at day 15, modelling and simulation will allow prediction of trametinib dosage regimens for children that will deliver target trametinib steady-state concentrations and exposure similar to adults.

Three dose levels are planned in pediatric subjects. In the absence of DLT, if the PK exposure is significantly lower than those achieved in adults, higher doses for subsequent cohorts may be modified in a protocol amendment in order to achieve PK target during dose escalation.

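### Section 3.2 gives 10 ng/mL as the mean adult trametinib trough at 2 mg; the protocol's own adult mean is 12.1 ng/mL, and 10 lies below its confidence interval

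*Protocol*

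**What the plan says.** The primary objective (Table 2-1) is a safe and tolerable dose giving exposure, measured as trough, similar to the recommended adult dose. Steady-state trough is a primary endpoint. The figure of 10 ng/mL appears in three roles.

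- **As an adult mean.** Section 3.2 asks for a paediatric mean trough that matches this adult reference: "mean steady state (Day 15) trough concentration of 10 ng/mL trametinib observed in adults at the recommended dose of 2 mg once daily". Section 3.2.2 also attributes the 10 ng/mL target to adults treated at the recommended dose.
- **As a confidence limit.** Section 1.2.1 gives its origin: "The lower bound of the 95% CI (approximately 10 ng/mL) of the adult mean" trough, to be used to guide the recommended Phase 2 dose (RP2D).
- **As a per-subject threshold.** Section 3.2.2 requires a Day 15 trough of 10 or more "in at least 80% of subjects in a cohort of at least 6 subjects (i.e.; 5/6 subjects"). Sections 3.2.4 and 3.2.5 apply an 80% criterion by age group.

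The adult data are given consistently elsewhere. In Section 3.2.1, "the Day 15 mean steady state" trough at 2 mg is "12.1 ng/mL (range 8.26-16.9; 95% CI=10.86-13.4"). Section 3.9.3.1 has "n=13, 8.3-16.9 ng/mL, CV=19%, 95%CI=10.86-13.4" around the same mean. Section 1.2.1 also prints the interval.

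Section 3.2.6, the extension for children under 6, notes that their median of 8.2 is below 10. It aims for a trough "similar to that achieved in adults", glossed as above 10 ng/mL. It states no 80% rule and declares the RP2D on safety and tolerability.

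**The concern.** The adult reference value for a primary endpoint is wrong in current design text. It is not the adult mean, and it falls outside the interval whose lower bound it is meant to represent: 10.86 has been rounded down to 10, and Section 3.2 then labels that figure the mean.

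What is at stake is the conclusion on similar exposure. A cohort mean of 10.0 to 10.85 satisfies the wording of Section 3.2 while lying below the adult interval. This matters most for children under 6, for whom 10 is used as a group-level benchmark with nothing further to meet.

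**Working it through.** **Inputs.** Adult mean 12.1 ng/mL (geometric, per Section 1.2.1), CV 19%, n=13 (Sections 1.2.1, 3.2.1, 3.9.3.1). Median trough at 0.025 mg/kg/day: 8.2 ng/mL under 6 years and 11.7 at 6-17 years (Table 3-3). Extension dose 0.032 mg/kg/day (Section 3.2.6).

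**1. Reproduce the adult interval.**
- Arithmetic scale: SE = 12.1 × 0.19/√13 = 0.638; 12.1 ± 1.96 × 0.638 = 10.85 to 13.35.
- Log scale: σ = √ln(1 + 0.19²) = 0.188; 12.1 × exp(±1.96 × 0.188/√13) = 10.92 to 13.40.

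Both match the stated 10.86-13.4 within rounding. With Student t on 12 df the lower limit is 10.71 (arithmetic) or 10.80 (log). No version reaches down to 10.

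**2. Place 10 against the adult figures.** 10/12.1 = 0.826, so 17% below the mean. 10/10.86 = 0.921, so 8% below the lower limit.

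**3. What the per-subject rule implies.** Assume lognormal troughs with the adult CV of 19%.
- Proportion of adults at or above 10 when the geometric mean is 12.1: Φ(ln 1.21/0.188) = 0.84. An 80% requirement is therefore close to what adults at 2 mg would show.
- Geometric mean needed for 80% of subjects to reach 10: 10 × exp(0.842 × 0.188) = 11.7, inside the adult interval.
- Chance that at least 5 of 6 reach 10, with p the per-subject probability: 6p⁵(1−p) + p⁶.

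| True geometric mean | p | P(at least 5 of 6) |
|---|---|---|
| 10.0 | 0.50 | 0.11 |
| 10.5 | 0.60 | 0.24 |
| 10.86 | 0.67 | 0.36 |
| 12.1 | 0.84 | 0.76 |

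If the paediatric CV is larger (30%, 40% or 50%, assumed), the geometric mean needed for 80% rises to 12.8, 13.8 or 14.9, and the chance of passing at 10.86 falls to 25%, 21% or 19%. The mean wording and the per-subject rule are thus different standards, and the per-subject rule is the stricter.

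**4. The under-6 extension.** Section 1.2.1 states dose proportionality for AUC and Cmax. If it also holds for trough (an assumption), the under-6 median at the extension dose projects to 8.2 × 0.032/0.025 = 10.5 ng/mL. That is above 10, below 10.86, and 10.5/12.1 = 0.87 of the adult mean. The 6-17 year median of 11.7 lies inside the adult interval, so either reference gives the same description.

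**The case against.** The strongest reply is that 10 does its real work as a per-subject threshold. Sections 3.2.2, 3.2.4 and 3.2.5 judge individuals, and step 3 shows that their 80% criterion demands roughly adult exposure. Section 1.2.1 discloses where 10 comes from, and an individual trough of 10 is well within the adult range of 8.26-16.9. This stands for the original Part A age groups and for 10 as a per-subject threshold. It does not reach Section 3.2.6, which states no such criterion.

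A reader might infer that the error lets an inadequate dose be selected, or that 10 versus 12.1 decides the under-6 dose. The documents do not support either. Every branch of Section 3.2.6 turns on DLT counts, an MTD overrides the PK criterion (Section 3.2), and 0.025 mg/kg/day was set on safety and tolerability (Section 3.9.3.1). Nor can one say that a low-exposure group would be reported as meeting the objective; only that the wording permits it.

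Two further replies have force. A confidence interval for the mean of 13 adults expresses precision and is not a similarity margin, so falling below 10.86 does not by itself show dissimilar exposure. And Sections 7.4 and 12.5.3 already plan a comparison with historical adult data, whose format may properly sit in the SAP. But the adult reference value is fixed in the protocol, and that is where it is wrong.

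**Conclusion.** The point holds as an inconsistent and partly wrong reference value, worth correcting but without effect on any dose decision. Section 3.2 misstates the adult mean by 2.1 ng/mL (17%), Section 3.2.2 carries the same attribution, and the figure lies 8% below the limit it is said to approximate. These statements rest only on the protocol's own numbers.

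The practical consequence is confined to how exposure is described. For children under 6, an average between 10.0 and 10.85 could be called similar to adults under Section 3.2.6 while lying below the adult interval. That this range is plausible (a projected 10.5) depends on trough being dose-proportional. The reassurance for the other Part A groups depends on lognormal troughs; a larger paediatric CV than the adult 19% makes the 80% rule more demanding, not less.

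**What to change.** - In Sections 3.2 and 3.2.2, give the adult reference as 12.1 ng/mL (95% CI 10.86-13.4).
- State that 10 ng/mL is a per-subject threshold lying below that interval, and reconcile Sections 1.2.1, 3.2, 3.2.2, 3.2.5 and 3.2.6 so that it has one meaning.
- Base the statement on similar exposure for each age group, including under 6, on the geometric mean Day 15 trough and its ratio to 12.1 with a confidence interval. Show the proportion of subjects at or above 10 beside it. The table layout can be left to the SAP.

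No dose rule changes. The cost is a few sentences and one summary table from Day 15 samples already collected. The downside is that the stated exposure result for the youngest group may look less favourable.

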3.2.1 Trametinib Dose Levels

The starting dose of trametinib (0.0125 mg/kg/day) is 50% of the recommended fixed dose in adults (2 mg once daily) based on an 80 kg adult ([Table 3-1](#)). In adults (n=2) after 15 days of continuous trametinib dosing (1 mg administered orally [PO] daily), the individual steady state C_{τ} was 8.44 and 19.1 ng/mL. The lowest trough concentration associated with an objective response in adults with melanoma was approximately 7 ng/mL; one complete response (1 mg dose) and one partial response (0.5 mg dose) were observed out of 12 subjects with C_{τ} of 7 ng/mL.

The second dose level (0.025 mg/kg/day) is equivalent to the recommended dose in adults (2 mg PO daily). In adults (n=13) receiving this dose, the Day 15 mean steady state C_{τ} was 12.1 ng/mL (range 8.26-16.9; 95% CI=10.86-13.4). In adults trametinib 2 mg PO daily on a continuous schedule is not associated with dose limiting toxicity and PK-PD modelling in adults with melanoma predict that 79% of subjects would exceed the mean target trough concentration over the entire dosing interval.

The third dose level (0.040 mg/kg/day) is equivalent to the MTD in adults (3 mg PO daily).

In the absence of establishing a pediatric MTD, if the PK target (Day 15 $C_{\tau} \geq 10$ ng/ml) is not achieved at the maximum dose level of 0.04 mg/kg/day, safety and PK data will be examined to consider amending the protocol for inclusion of additional higher dose levels.

Table 3-1 Trametinib Dose Levels for Part A

	Trametinib Oral Dosing
Dose Level 1 – Starting Dose	0.0125 mg/kg/day
Dose Level 2	0.025 mg/kg/day
Dose Level 3	0.04 mg/kg/day
Additional Dose Levels	Protocol amendment to explore additional dose according to observed PK values relative to target concentrations

3.2.2 Trametinib Dose Escalation

Subjects enrolled at each dose cohort will be observed for DLT during the first 28 days.

[figure not shown]
Dose escalation will occur according to [Table 3-2](#) and will be determined by both toxicity and observed PK values.

DLT Criteria for Escalation:

- Escalation may occur once the initial 3 subjects on Dose Level 1 or Dose Level 2 meet all of the following criteria:
 - have completed the first 28 days, and
 - have completed PK sampling on Day 15, and
 - are evaluable for toxicity (received at least 75% of prescribed (21/28) doses), and
 - have not experienced DLT attributable to trametinib in the first 28 days
- If one of the initial 3 subjects in the dose cohort experiences a DLT in the determinative period, the cohort will be expanded to 6 subjects. Dose escalation may occur once all 6 subjects at the current dose level meet all of the following criteria:
 - have completed the first 28 days, and
 - have completed PK sampling on Day 15, and
 - are evaluable for toxicity (received at least 75% of prescribed (21/28) doses), and
 - no more than one subject ($\leq 1/6$) experienced a DLT attributable to trametinib during the first 28 days
- If 2 or more of the initial 3-6 subjects enrolled at a dose level experience DLT, accrual will be suspended and the MTD will have been exceeded.

Table 3-2 Dose Escalation Procedure

Number of Subjects with DLT	Action
0 out of 3 subjects	Escalate to next dose level
1 out of 3 subjects	Accrue 3 additional evaluable subjects at current dose level for a total of 6 evaluable subjects
1 out of 6 subjects	Escalate to the next dose level
2 or more subjects in a dosing cohort (up to 6 subjects)	MTD has been exceeded. Expand prior dose level to at least 6 subjects

PK Criteria for Escalation:

Detailed PK sampling will be required on Day 15 for trametinib (see [Section 7.4.1](#)). Subjects who have a day 15 trametinib $C_{\tau} < 10$ ng/mL will be considered to have failed to reach the PK target. If more than 1 out of 3 to 6 patients at a dose level have failed to reach the PK target, and MTD criteria have not been met, dose escalation will continue. The Day 15 trametinib C_{τ} of all subjects in a dose level cohort will be compared to the target C_{τ} (10 ng/mL) in adults who were treated with the recommended dose in adults. In the absence of an MTD, the RP2D will be the PK target dose defined as the dose that meets the PK criteria for adequate exposure (Day 15 trametinib $C_{\tau} \geq 10$ ng/mL in at least 80% of subjects in a cohort of at least 6 subjects (i.e.; 5/6 subjects) treated at that dose level ([Appendix 9](#)).

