3.2.4 Part A: Age Group Expansion

Following the initial 3+3 dose escalation ([Section 3.2.2](#)), the dose will be confirmed and evaluated in the following specific age groups (age on day of consent):

- Infants and toddlers (age 1 month to < 2 years).

- Children (age 2 to ≤ 12 years).
- Adolescents (age >12 years to <18 years).

Note: For the purposes of this study, age 12 is considered to be the day of a subject's 12th birthday. The day after the 12th birthday, a subject is considered to be greater than 12 years.

Approximately 4 to 6 subjects may be enrolled in each age group and treated at the dose determined in the 3+3 escalation. Subjects in the age expansion cohorts will continue to be monitored for DLTs and PK as described for the initial dose escalation in Part A. The goal of the age expansion cohorts is to confirm the RP2D for each age group.

If the criteria for MTD are not met, and less than 80% of subjects in any age group (out of all subjects treated at that dose in that age group) achieve trametinib $C_{\tau} \geq 10$ ng/mL, subjects in that age cohort may not be enrolled on Parts B or C until the study sponsor and study team review all available safety and PK data.

Effect of sample size and PK sampling scheme on characterization of trametinib PK

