3.2.5 Definition of Recommended Phase 2 Dose (RP2D) of Trametinib

The RP2D is established by age groups (1 mo- < 2 years, 2 years to ≤ 12 years, > 12 years of age) as the dose level at which $< 33\%$ of subjects in the age group experience DLT and $> 80\%$ of subjects in the age group have trametinib $C_{\tau} \geq 10$ ng/mL.

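### The trametinib exposure target is a cohort mean in section 3.2 but a count of individuals in sections 3.2.2, 3.2.4 and 3.2.5, with 80% cut-offs that do not match, so the protocol does not say which statistic shows exposure similar to adults

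*Protocol*

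**What the plan says.** All references are to the Protocol.

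- **Section 3.2** describes the PK target dose as "defined as achieving in children a steady state (Day 15) mean trough concentration" that is "equivalent to a mean steady state (Day 15) trough concentration of 10 ng/mL trametinib observed in adults at the recommended dose". It adds that if an MTD is found, the MTD and not the PK criterion sets the RP2D.
- **Section 3.2.2** uses the same term for the dose at which the Day 15 trough is at least 10 ng/mL "in at least 80% of subjects in a cohort of at least 6 subjects (i.e.; 5/6 subjects) treated at that dose level", in the absence of an MTD. Its escalation trigger is also a count: "If more than 1 out of 3 to 6 patients at a dose level have failed to reach the PK target", and MTD criteria are not met, escalation continues.
- **Section 3.2.4** holds an age group out of Parts B and C, pending a sponsor and study-team review, when MTD criteria are not met and fewer than 80% reach 10 ng/mL. On size it says "Approximately 4 to 6 subjects may be enrolled in each age group".
- **Section 3.2.5** defines the RP2D by age group as the dose at which fewer than 33% have a DLT and strictly more than 80% "of subjects in the age group have trametinib" trough values of at least 10 ng/mL. It does not repeat the MTD override.
- **Sections 1.2.1 and 3.2.1** give the adult trough at 2 mg daily as 12.1 ng/mL (geometric mean in 1.2.1), CV 19%, n=13, range 8.26-16.9, 95% CI 10.86-13.4. Section 1.2.1 says that the lower bound of that interval, taken as about 10, guides the RP2D.

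**The concern.** One term carries two definitions, and they answer different questions. A mean criterion asks where the centre of the paediatric distribution lies. A count of individuals asks where its lower tail lies, so it also depends on the between-child spread and on the number of children. The value 10 ng/mL came from the uncertainty of an adult mean, but the count applies it as a floor for each child. Adults on the recommended dose had troughs down to 8.26, so some of them fall below that floor.

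There are two smaller mismatches. Section 3.2 attributes a mean of 10 ng/mL to adults on 2 mg, where section 3.2.1 gives 12.1. And 4 of 5 children, exactly 80%, would not trigger the hold in section 3.2.4 but would fail section 3.2.5.

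The primary objective (Table 2-1) is a safe and tolerable dose with exposure similar to the recommended adult dose, and steady-state trough is a primary endpoint. If the report says that this was or was not achieved, the answer can depend on which section is cited, and the protocol does not rank them.

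**Working it through.** **Inputs.** Adult mean 12.1 ng/mL, n=13, 95% CI 10.86-13.4 (section 3.2.1); CV 19% (sections 1.2.1 and 3.9.4); threshold 10 ng/mL; cohort of 6 and the 5/6 rule (section 3.2.2); age groups of 4 to 6 (section 3.2.4). Individual troughs are assumed lognormal or normal.

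**Step 1: do the adult figures agree with each other?**
- Normal scale: SD = 0.19 × 12.1 = 2.299; 12.1 ± 1.96 × 2.299/√13 = 10.85 to 13.35.
- Log scale: σ = √ln(1 + 0.19²) = 0.188; 12.1 × exp(±1.96 × 0.188/√13) = 10.92 to 13.40.
- The printed interval is reproduced to rounding, so mean, CV and n are coherent.

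**Step 2: share of individuals at or above 10 at exact adult exposure.**
- Lognormal: Φ(ln(12.1/10)/0.188) = 0.844.
- Normal: Φ((12.1 − 10)/2.299) = 0.819.

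**Step 3: the 5/6 count, P(≥5 of 6) = 6p⁵(1−p) + p⁶.**

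| True exposure | p | P(≥5 of 6) | Fails |
|---|---|---|---|
| Adult, lognormal | 0.844 | 0.763 | 24% |
| Adult, normal | 0.819 | 0.703 | 30% |
| Mean 10, lognormal with arithmetic mean 10 | 0.462 | 0.078 | 92% |
| Mean 10, normal, or lognormal with geometric mean 10 | 0.500 | 0.109 | 89% |

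If the printed interval was t-based, the log SD is 0.174, p = 0.864 and the adult failure rate is 19%.

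**Step 4: the same adult exposure under the mean rule of section 3.2.** The probability that the observed mean of six is at least 10 is Φ(√6 × ln(1.21)/0.188) = 0.993 on the log scale and 0.987 on the normal scale.

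**Step 5: the mean needed for 80% of individuals to reach 10.** Lognormal: 10 × exp(0.842 × 0.188) = 11.7. Normal: 10/(1 − 0.842 × 0.19) = 11.9. The count therefore implies a mean clearly above the 10 of section 3.2.

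**Step 6: strict >80% (section 3.2.5) in small groups.** With exactly 4 or 5 children, every child must reach 10. At adult exposure:
- 4 of 4: 0.844⁴ = 0.508 or 0.819⁴ = 0.451, so it fails 49-55% of the time.
- 5 of 5: 0.429 or 0.370, so it fails 57-63% of the time.

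**Step 7: the escalation trigger with 3 children.** At adult exposure, P(at least 2 of 3 below 10) = 0.065 (lognormal) or 0.086 (normal).

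**Illustration.** Section 3.9.3.1 gives a median of 11.7 ng/mL in patients aged 6-17 years at 0.025 mg/kg/day, which is 97% of 12.1. The implied share at or above 10 is about 80% if the paediatric CV is 19%, and 66-74% if it is 25-40%. The paediatric CV is an assumption, and this age band is not one of those in section 3.2.5. Exposure close to the adult mean would sit on or below the 80% line.

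**The case against.** The strongest reply is that the rule has been used up. Section 3.2 gives precedence to the MTD, and section 3.2.2 applies the count only without one. The 0.04 mg/kg/day dose exceeded the MTD, and 0.025 mg/kg/day was set on safety and tolerability (section 3.9.3.1). The Part A extension also declares its RP2D on safety and tolerability (section 3.2.6), and all cohorts are closed (Amendment 9 rationale). That stands, and it removes any effect on dosing.

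It is also fair that Table 2-1 contains no 80% rule and that section 12.5.3 already plans a comparison with historical adult data. A reader might infer that the count decides whether the primary objective is met. The documents present it as a dose-selection rule. What remains open is which statistic defines similar exposure.

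The disagreement runs mostly one way. A cohort with 5 of 6 at or above 10 will nearly always have a mean above 10, so the count is the stricter rule.

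Three stronger readings are not supported:

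- A reader might take section 3.2.1, where modelling is said to "predict that 79% of subjects would exceed the mean target trough concentration over the entire dosing interval", as the adult pass rate for the count. The text does not tie that figure to a Day 15 trough of 10 ng/mL, so it is not used here.
- A reader might infer that adult-equivalent exposure would push escalation in a quarter or more of cohorts. That needs six children. Cohorts start with three, where the probability is 6-9%.
- A reader might infer that age groups generally need every child above 10. Section 3.2.4 counts all subjects treated at that dose in the age group, and section 3.10.1 adds the Part A subjects already at the RP2D. The older groups can therefore exceed 4 to 6. Below 80%, section 3.2.4 calls for a review of the data and does not reject the dose.

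Appendix 9, cited in section 3.2.2 for the PK criteria, was not in the text available here and may carry further detail.

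**Conclusion.** The point holds in a limited form. The current text defines the PK target dose by a mean in section 3.2 and by a count in section 3.2.2. Sections 3.2.4 and 3.2.5 treat exactly 80% differently, and section 3.2.5 omits the MTD override. The definitions differ materially: a true mean of 10 passes 5/6 in about 8-11% of cohorts. Exact adult exposure fails 5/6 in about 24-30%, and fails the strict >80% in about 49-63% if an age group has exactly 4 or 5 subjects.

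These rates assume normal or lognormal troughs, a paediatric spread equal to the adult CV of 19%, and adult figures from 13 people, so they are approximate. The contradiction itself needs no assumption.

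The consequence is confined to how the similar-exposure objective is reported. Nothing here shows that a dose was wrongly chosen, and this review does not say which dose or rule is right. It deserves correction before the final analysis, but it does not threaten the validity of the trial.

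**What to change.** - Reconcile sections 3.2, 3.2.2, 3.2.4 and 3.2.5 to one stated definition of the exposure target. It should cover mean or count, at least 80% or more than 80%, the denominator, and whether the MTD override applies throughout. Correct or explain the adult mean of 10 in section 3.2 against 12.1 in section 3.2.1.
- In the final analysis, report the geometric mean Day 15 trough by age group and dose, with a confidence interval, as a ratio to the adult 12.1 ng/mL.
- Show the share of children at or above 10 ng/mL beside the roughly 82-84% implied by the adult data, labelled as approximate and based on n=13.

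The cost is wording in four sections and one additional PK summary from data already collected. No dose, visit or sample changes. The trade-off is that similar exposure is then described by an estimate with an interval, beside or in place of a pass/fail count. Settling the definition before the final results are seen avoids choosing it afterwards.
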